10.3 Response evaluation

The response will be evaluated after the induction cycles 1, 3, 5, 7 and 9; after every maintenance cycle during the first year and thereafter every 2 maintenance cycles. Response evaluation should also be done when taken off protocol treatment and during follow up every 8 weeks untill second progression and every 6 months thereafter. Response will be evaluated according to appendix C.

10.4 Quality of Life assessment

Quality of life (QoL) will be assessed by means of the following questionnaires:

EORTC QLQ-C30 questionnaire

The QLQ-C30 is a multidimensional, cancer-specific quality-of-life questionnaire developed by the European Organization for Research and Treatment of Cancer (EORTC) Study Group on Quality of Life for use in international clinical trial settings. The questionnaire is designed for use with a wide range of cancer patient populations, irrespective of specific diagnosis. The QLQ-C30 includes 5 functional scales (physical, role, emotional, social and cognitive functioning), 3 symptom scales (fatigue, pain, and nausea and vomiting), a global health status/quality of life scale and a number of single items assessing additional symptoms (dyspnoea, sleep disturbance, constipation and diarrhea) and perceived financial impact. For the majority of the QLQ-C30 items a 4-point Likert-type response scale is used. Exceptions are the items for the global quality of life scale (where a 7-point scale is used). All subscale and individual item responses are linearly converted to 0 to 100 scales. For the functional and global quality of life scales, a higher score represents a better level of functioning. For the symptom scales and items, a higher score reflects a greater degree of symptomatology.

EORTC QLQ-MY20

This questionnaire measures specific aspects of multiple myeloma, i.e. specific pain complaints.

HOVON participants

Collection of the QoL questionnaires will be performed in the following manner:

A QoL coordinator will be assigned in each participating center. The QoL questionnaire collection is left to the responsibility of the QoL coordinator.

During informed consent the patient will be asked to participate in the quality of life part of this study. If the patient gives consent, the QoL coordinator is notified by e-mail as soon as a patient is registered at the HOVON Data Center (HDC). Patient study number, date of birth and date of registration are mentioned in this e-mail. The baseline questionnaire will be handed to the patient by the QoL coordinator. At subsequent time points the coordinator will be reminded in time to hand over the questionnaire at the correct date. The QoL coordinator will collect the questionnaire from the patient and send it to HDC. If a QoL questionnaire has not been received by HOVON Data Center within 14

days of the expected date, a reminder/request will be sent to the local QoL coordinator to collect and send in the questionnaire.

NMSG participants

The patients are registered at the HOVON data center. If the patient has signed the consent to participate in the QoL study, he/she will be asked to fill in the baseline questionnaire which is sent to QoL center at Ullevål Hospital, Oslo. All centers will be provided with questionnaires and prestamped reply envelopes. When the first questionnaire is received at the QoL center, new questionnaires with prestamped envelopes will be sent out at regular intervals. The procedure in the Dutch and NMSG branch is similar except that Ullevål Hospital will be the Nordic QoL center.

Quality of life will be measured:

- at entry
- after cycle 3
- after cycle 6
- after cycle 9 or earlier in case of premature discontinuation of induction treatment
- at 6 months after start of maintenance therapy
- at 12 months after start of maintenance therapy
- at discontinuation of maintenance therapy

The quality of life measurements will be stopped when patient goes off protocol treatment.

10.5 Central review

10.5.1 Cytogenetic review

FISH analysis is required in all patients at diagnosis/start of study. The following cytogenetic abnormalities will be evaluated as prognostic variables del1p, gain 1q, t(4;14)(p16;q32), t(14;16)(q32;q23), t(11;14)(q13;q32), del13q/13-, del17p and hyperdiploidy (at least 2 of the chromosomes 5, 9, 11 and 15 should be analyzed). Conditions for FISH will be according to the EMN guidelines (Ross et al., Haematologica 97, 1272-1277 (2012))

The cytogenetic review concerns a review of the original FISH data, cross checking original FISH data, data on CRF and data in the database

10.6 Side studies

Genomic profiling, β 5 subunit mutation analysis & single nucleotide polymorphism (SNP) analysis

Gene expression profiling, miRNA profiling, sequencing, β5 subunit mutation analysis and SNP analysis will be performed to further characterize MM subgroups at the molecular level, to find new

biomarkers with prognostic value, to elucidate mechanisms of drug resistance & disease progression and identify SNPs related to treatment outcome and side-effects. Bone marrow samples and peripheral blood will be drawn before start and during treatment. Samples will be sent to the Erasmus MC as per instructions in Appendix I. In addition, we aim to include additional studies aimed at elucidating aberrancies on DNA, RNA and protein level, including copy number analysis and transcription factor binding studies. Optional studies of peripheral blood include in depth analysis of immunoglobulins as well as cytokines.

Minimal Residual Disease

In this trial the importance of flowcytometric Minimal Residual Disease (MRD) negativity will be investigated in a correlative study. Patients who are immunofixation negative in serum and urine need to undergo a bone marrow aspirate in order to confirm flowcytometric MRD negativity. A bone marrow puncture needs to be performed at the first response evaluation moment at which there is immunofixation negativity. Material for MRD has to be obtained only once, at the first immunofixation negative result; there is no sequential analysis of MRD status in this trial. Also see appendix I.

FDG-PET study

Recently it was found that the extent of the disease as defined by FluoroDeoxyGlucose - Positron Emission Tomography (FDG-PET) was correlated with clinical outcome of transplant-eligible patients. However, data in non-transplant eligible patients are lacking. Therefor, the prognostic value of FDG-PET at diagnosis and following induction therapy will be determined. To this end the extent of bone disease (number of lesions) and several Standard Uptake Value (SUV) metrics reflecting FDG uptake at diagnosis will be related to PFS and OS. In addition, the prognostic value of normalisation of FDG uptake after induction therapy will be determined.

11 Withdrawal of patients or premature termination of the study

11.1 Specific criteria for withdrawal of individual patients

Patients can leave the study at any time for any reason if they wish to do so without any consequences. The investigator can decide to withdraw a patient from protocol treatment for urgent medical reasons. Specific criteria for withdrawal are:

- Death
- Excessive toxicity
- Progression during treatment
- No compliance of the patient
- Refusal to continue protocol treatment

11.2 Follow up of patients withdrawn from treatment

Patients who are withdrawn from treatment for other reasons than death will be followed as described in 10.2 for follow up.

For patients who are withdrawn from treatment because in hindsight they did not fulfil the eligibility criteria (at time of enrolment (see 8.1) or at time of randomization (see 8.2)), data will be collected until 30 days after the last protocol treatment given. SAE information will be collected as described in 12.3. At the time of withdrawal, all study procedures outlined for the *off protocol treatment* visit should be completed. The primary reason for patient's withdrawal from the study should be recorded in the source documents and CRF.

No further information will be collected for patients who have withdrawn their consent. If a patient withdraws consent please consult HOVON Data Center.

Patients who are withdrawn from protocol treatment will receive medical care according to local practice.

11.3 Premature termination of the study

The sponsor may decide to terminate the study prematurely based on the following criteria:

- There is evidence of an unacceptable risk for study patients (i.e. safety issue);
- There is reason to conclude that it will not be possible to collect the data necessary to reach the study objectives and it is therefore not ethical to continue enrolment of more patients; for example insufficient enrolment that cannot be improved.
- The DSMB recommends to end the trial based on viable arguments other than described above

The sponsor will promptly notify all concerned investigators, the Ethics Committee(s) and the regulatory authorities of the decision to terminate the study. The sponsor will provide information regarding the time lines of study termination and instructions regarding treatment and data collection of enrolled patients.

12 Safety

12.1 Definitions

Adverse event (AE)

An adverse event (AE) is any untoward medical occurrence in a patient or clinical study administered a medicinal product and which does not necessarily have a causal relationship with the treatment.

An AE can therefore be any unfavorable and unintended sign (including an abnormal laboratory finding), symptom, or disease temporally associated with the use of a medicinal (investigational) product, whether or not considered related to the medicinal (investigational) product.

Serious adverse event (SAE)

A serious adverse event is defined as any untoward medical occurrence that at any dose results in:

- ♦ Death
- A life-threatening event (i.e. the patient was at immediate risk of death at the time the reaction was observed) It does not refer to an event which hypothetically might have caused death if it were more severe)
- Requires inpatient hospitalization or prolongation of an existing hospitalization (see clarification in the paragraph below on planned hospitalizations).
- Significant / persistent disability or incapacity (disability is defined as a substantial disruption of a person's ability to conduct normal life functions).
- ♦ A congenital anomaly / birth defect
- Any other medically important condition (i.e. important adverse reactions that are not immediately life threatening or do not result in death or hospitalization but may jeopardize the patient or may require intervention to prevent one of the other outcomes listed above, including suspected transmission of infectious agents by a medicinal product). Examples of such medical events include second primary malignancies, allergic bronchospasm requiring intensive treatment in an emergency room or at home, blood dyscrasias or convulsions that do not result in inpatient hospitalization, or the development of drug dependency or drug abuse; any organism, virus, or infectious particle (eg, prion protein transmitting Transmissible Spongiform Encephalopathy), pathogenic or nonpathogenic, is considered an infectious agent.

Note that ANY death, whether due to side effects of the treatment or due to progressive disease or due to other causes is considered as a serious adverse event and must be reported as described in 12.3.1.

Suspected unexpected serious adverse reaction (SUSAR)

All **suspected** Adverse Reactions which occur in the trial and that are both **unexpected** and **serious**. Suspected adverse reactions (AR) are those AEs of which a reasonable causal relationship to any dose administered of the investigational medicinal product and the event is suspected. Unexpected adverse reactions are adverse reactions, of which the nature, or severity, is not consistent with the applicable product information (e.g. Investigator's Brochure for an unapproved IMP or Summary of Product Characteristics (SPC) for an authorised medicinal product).

12.2 Adverse event

12.2.1 Reporting of adverse events

Adverse events will be reported from the first study-related procedure until 30 days following the last dose of any drug from the protocol treatment schedule or until the start of subsequent systemic therapy for the disease under study, if earlier.

Adverse events occurring after 30 days should also be reported if considered at least possibly related to the investigational medicinal product by the investigator.

Adverse Events have to be reported on the Adverse Events CRF. Adverse Events will be scored according to the NCI Common Terminology Criteria for Adverse Events, version 4.0 (see appendix E). The investigator must determine both the intensity of the event and the relationship of the event to study drug administration.

Pre-existing conditions will be collected on the baseline concomitant diseases CRF, i.e. active (symptomatic) diseases of CTCAE grade ≥ 2 diseases under treatment, chronic diseases and long term effects of past events as present at the time of baseline assessment.

All Adverse Events have to be reported, with the exception of.

- A pre-existing condition that does not increase in severity; the pre-existing condition should be reported on the baseline concomitant diseases CRF
- ◆ AE's of CTCAE grade 1, however polyneuropathy grade 1 has to be reported
- An abnormal laboratory value that does not lead to discontinuation or delay in treatment, or dose modification, or therapeutic intervention, and is not considered by the investigator to be a clinically significant change from baseline
- Relapse/progression of the disease under study; complications as a result of disease progression remain reportable Adverse Events

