- To determine toxicity, polyneuropathy and hematological toxicity in specific, during induction and maintenance treatment with xazomib citrate or placebo
- To determine progression free survival and overall survival from registration
- To compare the efficacy between maintenance

- treatment with ixazomib citrate versus placebo determined as overall survival from randomization
- To determine the efficacy of maintenance therapy with ixazomib citrate determined as an increase in response during maintenance treatment with ixazomib citrate versus placebo
- To determine efficacy of induction therapy determined as time to response
- To determine feasibility, defined as discontinuation rate due to toxicity, during induction and maintenance treatment with ixazomib citrate or placebo
- To determine time to next treatment
- To determine PFS on second line therapy
- To determine Quality of Life during induction therapy and maintenance treatment with ixazomib citrate versus placebo
- To identify clinical, imaging-related and molecular prognostic markers prognostic and predictive for outcome and toxicity
- To determine second primary malignancies (SPM).

Study design

Prospective, multicenter, randomized double blind placebo controlled phase II

Patient population

Previously untreated symptomatic patients with MM age ≥ 66 years or patients ≤ 65 years and ineligible for high dose therapy and peripheral stem cell transplantation

Intervention

Following induction therapy half of the patients will receive 4 mg of ixazomib citrate capsules as a maintenance therapy until progression and the other half of patients will receive placebo capsules as a maintenance therapy until progression

Duration of treatment

Expected duration of induction treatment: 9 months

Maintenance therapy with ixazomib citrate or placebo will be given until progression

All patients will be followed 8 years after registration

randomize 94 patients. See section 14.1 for detailed

information.

Expected duration of accrual 18 months

Main study endpoints Progression free survival from randomization

Response rate after induction treatment

Benefit and nature and extent of the burden and isks associated with participation

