- To determine toxicity, polyneuropathy in specific, during induction treatment and maintenance treatment with ixazomib citrate or placebo
- ♦ To determine progression free survival and overall survival from registration
- ♦ To compare the efficacy between maintenance treatment with ixazomib citrate versus placebo determined as overall survival from randomization
- To determine the efficacy of maintenance therapy determined as an improvement in response during maintenance treatment with ixazomib citrate or placebo
- ♦ To determine efficacy of induction therapy determined as time to response
- ♦ To determine feasibility, defined as discontinuation rate due to toxicity, during induction treatment and maintenance treatment with ixazomib citrate or placebo
- To determine time to next treatment
- To determine PFS on second line therapy
- To determine Quality of Life during induction treatment and maintenance therapy with Ixazomib or placebo
- To identify clinical, imaging-related and molecular markers prognostic and predictive for outcome and toxicity
- To establish second primary malignancies (SPM)

7 Study design

This is a multicenter phase II clinical trial, with upfront registration and late double-blind, placebocontrolled, maintenance randomization. Details of all treatments (dose and schedule) are given in section 9 and appendix F, G and H.

- 1. Patients will be registered, and then they will be treated with 9 cycles of induction therapy* with ixazomib citrate— thalidomide low dose dexamethasone;
- 2. After induction, patients eligible for randomization will be randomized double-blind between maintenance treatment with ixazomib citrate versus placebo.

The primary objective of this trial is to assess whether maintenance with ixazomib citrate improves PFS (calculated from date of randomization) as compared to placebo. This is used for the sample size calculation. This trial is therefore a superiority trial.

* Randomization and subsequent start of maintenance therapy is allowed after a minimum of 6 induction cycles as described in 8.2.1.

8 Study population

All eligible patients have to be registered before start of treatment. After the induction treatment patients will be randomized.

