12.3 Serious Adverse Events

12.3.1 Reporting of serious adverse events

Serious Adverse Events (SAEs) will be reported from the first study-related procedure until 30 days following the last dose of any drug from the protocol treatment schedule or until the start of subsequent systemic therapy for the disease under study, if earlier.

Serious Adverse events occurring after 30 days should also be reported if considered at least possibly related to the investigational medicinal product by the investigator.

SAEs must be reported by **investigators** to the HOVON Data Center by fax **within 24 hours** after the event was known to the investigator, using the SAE report form provided. This initial report should contain a minimum amount of information regarding the event, associated treatment and patient identification, as described in the detail in the instructions for the SAE report form. Complete detailed information should be provided in a follow-up report within a further 2 business days, if necessary. When possible, signs and symptoms indicating a common underlying pathology should be noted as one comprehensive event.

Any clinically relevant deterioration in laboratory assessments or other clinical finding is considered an AE (also see 12.1 and 12.2.1)

The following events are not considered to be a Serious Adverse Event:

- Relapse/progression of the disease under study; complications as a result of disease progression remain reportable Serious Adverse Events
- Hospitalization for protocol therapy administration. Hospitalization or prolonged hospitalization for a complication of therapy administration will be reported as a Serious Adverse Event.
- Hospitalization for diagnostic investigations (e.g., scans, endoscopy, sampling for laboratory tests, bone marrow sampling) that are not related to an adverse event. Hospitalization or prolonged hospitalization for a complication of such procedures remains a reportable serious adverse event.
- Prolonged hospitalization for technical, practical, or social reasons, in absence of an adverse event.

Hospitalization for a procedure that was planned prior to study participation (i.e. prior to registration or randomization). This should be recorded in the source documents. Prolonged hospitalization for a complication of such procedures remains a reportable serious adverse event.

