14.2.2 Toxicity analysis

The analysis of treatment toxicity will be done primarily by tabulation of the incidence of adverse events CTCAE grade 2 or more by induction cycle, and also for maintenance and placebo. Data from all subjects who receive any study drug will be included in the safety analyses. In the by-subject analysis, a subject having the same event more than once will be counted only once. Adverse events will be summarized by worst CTCAE grade.

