The grading of adverse events will be done using the NCI Common Terminology Criteria for Adverse Events, CTCAE version 4.0. A complete document may be downloaded from the HOVON website:

http://www.hovon.nl (under Trials > General information about studies)

F. Intake of ixazomib citrate and management of ixazomib citrate toxicity during an induction cycle and maintenance therapy

Ixazomib citrate will be given as a single, oral dose of 4.0 mg weekly (Days 1, 8, and 15) for 3 weeks, followed by 1 week without study drug in a 28-day cycle. Patients should be instructed to swallow ixazomib citrate/placebo capsules whole with water and not to break, chew, or open the capsules. Ixazomib citrate should be taken on an empty stomach, at least 1 hour before or no sooner than 2 hours after a meal. The capsule should be swallowed with a sip of water. A total of approximately 150 mL of water should be taken with the capsules. Missed doses can be taken as soon as the patient remembers as long as the next scheduled dose is 72 hours or more away. A double dose should not be taken to make up for a missed dose. If the patient vomits after taking a dose, the patient should not repeat the dose but should resume dosing at the time of the next scheduled dose.

[figure not shown]
Dose levels

Dose Levels for ixazomib citrate during Induction and Maintenance Therapy

Dose Levels	Ixazomib citrate
Starting Dose	4 mg once weekly on days 1,8 and 15 every 28 days
Dose Level -1	3 mg once weekly on days 1,8 and 15 every 28 days
Dose Level -2	2,3 mg once weekly on days 1,8 and 15 every 28 days
Dose Level -3	discontinue (off protocol treatment)

Dosage adjustments for hematologic toxicity.

See flow sheet and table at next pages.

Dose adjustments for hematological toxicities

Criteria	Action
Within-Cycle Dose Modifications - If platelet count ≤ 30 × 109/L or ANC ≤ 0.50 × 109/L on a MLN9708 dosing day (other than Day 1)	 MLN9708 dose should be withheld. Complete blood count (CBC) with differential should be repeated within one week or earlier at the discretion of the physician until the ANC ≥ 1.0x10⁹/L and/or platelet counts ≥ 75x10⁹/L. Upon recovery within the cycle, MLN9708 may be reinitiated with 1 dose level reduction.

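### The laboratory exemption in adverse-event reporting can leave out cytopenias that the toxicity table is meant to count

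*Protocol*

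**What the plan says.** Section 12.2.1 starts from the rule that all adverse events are reported and then lists exceptions. One is "An abnormal laboratory value that does not lead to discontinuation or delay in treatment, or dose modification, or therapeutic intervention". A second condition in the same sentence must also hold: "and is not considered by the investigator to be a clinically significant change from baseline". No grade limit is attached. A separate exception covers "AE's of CTCAE grade 1, however polyneuropathy grade 1 has to be reported". No similar clause exists for blood counts. Section 12.3.1 adds: "Any clinically relevant deterioration in laboratory assessments or other clinical finding is considered an AE".

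On objectives, the synopsis has "To determine toxicity, polyneuropathy and hematological toxicity in specific, during induction and maintenance treatment". Section 6 is narrower and singles out only neuropathy: "To determine toxicity, polyneuropathy in specific, during induction treatment and maintenance treatment with ixazomib citrate or placebo". The synopsis rationale and section 5.1.1 hypothesise less haematological toxicity than with standard therapy.

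On analysis, section 13.2 defines the safety endpoint by the type, frequency and severity of adverse events. Section 14.2.2 analyses toxicity primarily by "tabulation of the incidence of adverse events CTCAE grade 2 or more by induction cycle", and likewise for maintenance and placebo.

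On treatment consequences, Appendix F withholds ixazomib on a dosing day other than Day 1 "If platelet count ≤ 30 × 109/L or ANC ≤ 0.50 × 109/L". Section 9.1.2 requires ANC of at least 1.0 and platelets of at least 75 (× 10⁹/L) to start the next cycle.

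**The concern.** Reportability of a laboratory event depends on what was done about it and on whether the investigator calls it significant, not on its grade. Grade 1 events are already exempt under their own bullet. The laboratory exemption therefore makes a difference only at grade 2 or more, which is the range that section 14.2.2 tabulates.

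At stake is the meaning of the haematological rows in the toxicity table. They may describe cytopenias that were acted on or judged important, rather than cytopenias that occurred. Sites may also differ: section 9.1.3 leaves growth factors to institutional practice. The same count becomes reportable at a site that treats it and need not be at a site that watches it. The DSMB reports in section 14.3 also describe adverse events by grade, so the same gap could carry over to them. A later analysis plan cannot restore events that were never collected.

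**Working it through.** The protocol gives no figure for this loss, so there is none to reproduce. The check has two parts.

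**1. Which cytopenias can escape?** I set the reporting rule beside the treatment rules. The flow sheet in Appendix F was not readable in my copy, so this rests on the tables and text.

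| Situation in a cycle | Consequence in the protocol | Must it be reported? |
|---|---|---|
| Platelets ≤ 30 or ANC ≤ 0.50 on a later dosing day | Dose withheld (Appendix F) | Yes |
| Counts below 75 or 1.0 at the planned start of the next cycle | Delay (9.1.2) | Yes |
| Toxicity after the Day 15 dose, recovered by the next cycle | Appendix F row for all haematologic toxicities: reduction at the next cycle; no count limit printed | Yes, where the row applies |
| Neutropenia treated with growth factor | Therapeutic intervention (9.1.3 permits it) | Yes |
| Platelets above 30 but below 50 in induction | Aspirin or LMWH stopped (9.1.3) | Unclear whether this counts as an intervention |
| ANC above 0.50 and below 1.0, or platelets from 50 to below 75, seen by the Day 15 dose, recovered, untreated | None required for ixazomib; thalidomide and dexamethasone are not reduced for haematological toxicity (Appendices G and H) | Only if judged clinically significant |

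The last row is the gap. These counts are not trivial by the protocol's own standard, since they are too low to start a cycle. I assume that some of them are grade 2 or more; Appendix E adopts CTCAE 4.0 without printing the boundaries.

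**2. How large could the effect be?** Let p be the true share of patients with such toxicity, and f the share of those patients whose only events fall under the exemption. Then

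recorded rate = p × (1 − f), shortfall = p × f, SE = √(p(1 − p)/n).

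The 142 registered patients come from section 14.1. Both p and f are assumptions.

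| p | SE, n = 142 | f = 0 | f = 10% | f = 25% | f = 50% |
|---|---|---|---|---|---|
| 20% | √(0.2 × 0.8/142) = 3.4 points | 20% | 18% | 15% | 10% |
| 40% | √(0.4 × 0.6/142) = 4.1 points | 40% | 36% | 30% | 20% |

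The shortfall is 2, 5 and 10 points at p = 20%, and 4, 10 and 20 points at p = 40%. At f = 25% it already exceeds one standard error in both rows. With f = 0 there is no bias.

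In blinded maintenance, with the same f in both arms, the recorded difference is (p₁ − p₂)(1 − f). For assumed rates of 30% and 10% and f = 25%, this is 22.5% − 7.5% = 15 points instead of 20.

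**The case against.** The strongest reply is that the exemption needs two conditions, and the second leaves every significant abnormality reportable. Section 12.3.1 points the same way. A reader who stops at the first condition might infer that every laboratory abnormality without a treatment consequence is exempt, and that haematological toxicity is therefore under-recorded. The text does not support that: it shows a risk that depends on investigator judgement, not an established loss. What remains is that clinical relevance in 12.3.1 is again a judgement, so it does not close the gap.

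The gap is also narrower than it first looks, because the Appendix F reduction row and growth-factor use make further events reportable. That stands, and the table above allows for it.

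A reader might want to size the loss from Table 5-4, which shows 17% neutropenia. That is not sound. The row label is missing in my copy, and those patients were heavily pretreated (median 4 prior lines). The newly diagnosed combination study in Table 5-6 does not list neutropenia among drug-related grade 3 or higher events seen in at least 2 patients, so at most 1 of 65 had it.

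Third, the hypothesis of less toxicity is not formally tested, and section 14.2.4 calls everything except the primary analysis hypothesis-generating. Induction has no concurrent control, so a lower recorded rate favours the hypothesis only to the extent that the external comparator was recorded more completely, which the protocol does not show. In maintenance the rule is the same in both arms. These points limit the consequence but do not remove it.

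Finally, section 16.1 gives only a minimum CRF list and 14.2.2 says primarily, so grading from blood counts is not excluded. Neither section provides for it, however, and the CRF list does not name counts.

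**Conclusion.** The point holds as a risk of understatement. A cytopenia with no treatment consequence that is judged not clinically significant need not be reported, whatever its grade. Those most exposed stay above the withholding limits, recover before the next cycle and are untreated. The haematological part of the grade 2 or more table may therefore be too low and may vary between sites.

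Any loss can only lower the recorded rate. In induction that is the direction of the synopsis hypothesis. In blinded maintenance, with an equal omitted share in both arms, it can only shrink the absolute difference. The size cannot be determined from the protocol; the 2 to 10 and 4 to 20 point shortfalls rest on assumed rates and an assumed omitted share of 10 to 50%. The primary PFS comparison is not affected. This is a cheap improvement to data collection, not a flaw that threatens the trial.

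**What to change.** Either of two changes would do.

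1. In section 12.2.1, add to the laboratory exemption, on the model of the polyneuropathy clause: *however, neutropenia, thrombocytopenia and anaemia of CTCAE grade 2 or more have to be reported regardless of consequence.*
2. Record the worst scheduled neutrophil, platelet and haemoglobin value per cycle on the CRF, and have section 14.2.2 derive haematological grades from these by cycle and by arm.

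The second removes judgement from grading. It sees only what is measured: section 10.2 schedules counts every 2 weeks in induction (every 4 weeks is allowed if cycles 1 to 3 show no haematological toxicity), and every cycle, later every 8 weeks, in maintenance.

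Neither change alters a dose or a clinical rule or needs an extra blood sample. The cost is a little more data entry and higher reported haematological toxicity rates.
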